5.6.4.3 Physical Examination

Any relevant findings at screening are included as part of the patient's medical history. Any changes seen after screening that are indicative of an AE are to be recorded as such on the AE form and included as part of the AE summaries.

Additionally, height and weight are recorded as part of the physical examination. Height and weight will be summarized and listed together with the vital signs parameters.

Incidence of patients with a physical examination indicative of a medical condition at Visit 1 and indicative of an adverse event after Visit 1 will be summarized by treatment arm and visit.

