2.2 Secondary Objectives

Blinded Phase:

- To evaluate the effect of GWP42003-P compared with placebo on antiepileptic measures.
- To evaluate the effect of GWP42003-P on growth and development (in patients less than 18 years old) compared with placebo.
- To evaluate the effects of GWP42003-P on quality of life compared with placebo.
- To evaluate the safety and tolerability of GWP42003-P compared with placebo.

Open-label Extension:

- To evaluate the long term effects of GWP42003-P, as add-on therapy, on antiepileptic measures.
- To evaluate the long term effect of GWP42003-P on growth and development (in patients less than 18 years old).
- To evaluate the long term effects of GWP42003-P on quality of life.
- To evaluate the long term safety and tolerability of GWP42003-P.

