3.3.2 Secondary Efficacy Endpoints

Blinded Phase:

The following endpoints will be compared between treatment arms over the 16-week, double-blind treatment period (all changes relative to baseline):

Key:

1. Number of patients considered treatment responders defined as those with a $\geq 50\%$ reduction in TSC-associated seizure frequency (see Section 5.1.3.7).
2. Change in Caregiver Global Impression of Change (CGIC) or Subject Global Impression of Change (SGIC) score.
3. Change in total seizures.

Other:

Antiepileptic Efficacy Measures:

- Number of patients considered treatment responders defined as those with a $\geq 25\%$, $\geq 50\%$, $\geq 75\%$ or 100% reduction in TSC-associated seizure frequency.
- Number of patients experiencing a $> 25\%$ worsening, $- 25$ to $+ 25\%$ no change, $25-50\%$ improvement, $50-75\%$ improvement or $> 75\%$ improvement in TSC-associated seizure frequency.
- Change in number of TSC-associated seizure-free days.
- Change in number of 'other' seizures (absence, myoclonic, focal sensory and infantile/epileptic spasms).

Growth and Development (in patients less than 18 years old):

- Change in serum insulin-like growth factor-1 (IGF-1) levels.
- Change in Tanner Staging score (for patients aged 10–17 [inclusive]).

Quality of Life:

- Changes in the Quality of Life in Childhood Epilepsy (QOLCE; patients 2–18 years) or Quality of Life in Epilepsy (QOLIE-31-P; patients 19+ years) score.
- Change in Physician Global Impression of Change (PGIC) score.

Safety and Tolerability:

- AEs.
- Clinical laboratory parameters.
- 12-lead electrocardiogram (ECG).
- Physical examination parameters.
- Vital signs.
- Columbia-Suicide Severity Rating Scale (C-SSRS: 19+ years) or C-SSRS Children's (6–18 years) score, where applicable.
- Number of inpatient hospitalizations due to epilepsy.
- Abuse liability.
- Effects on menstruation cycles (in females).

Open Label Extension:

The following endpoints will be assessed relative to the pre-randomization baseline of the blinded phase:

Key:

- Percentage change in number of TSC-associated seizures (average per 28 days).
- Number of patients considered treatment responders defined as those with a $\geq 50\%$ reduction in TSC-associated seizure frequency.
- Change in CGIC or SGIC score.
- Change in total seizures.

Other:

Antiepileptic Efficacy Measures:

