- Number of patients considered treatment responders defined as those with a $\geq 25\%$, $\geq 50\%$, $\geq 75\%$ or 100% reduction in TSC-associated seizure frequency.
- Number of patients experiencing a $> 25\%$ worsening, $- 25$ to $+ 25\%$ no change, $25-50\%$ improvement, $50-75\%$ improvement or $> 75\%$ improvement in TSC-associated seizure frequency.
- Change in number of TSC-associated seizure-free days.
- Change in number of 'other' seizures (absence, myoclonic, focal sensory and infantile/epileptic spasms).

Growth and Development (patients less than 18 years):

- Change in serum IGF-1 levels.
- Change in Tanner Staging score (for patients aged 10–17 [inclusive]).

Quality of Life:

- Changes in the QOLCE (patients 2–18 years) or QOLIE-31-P (patients 19+ years) score.
- Change in PGIC score.

Safety and Tolerability:

- Clinical laboratory parameters.
- ECG.
- Physical examination parameters (including height and weight).
- Vital signs.
- C-SSRS (19+ years) or C-SSRS Children's (6–18 years) score, where applicable.
- Number of inpatient hospitalizations due to epilepsy.
- Abuse liability.
- Effects on menstruation cycles (in females).

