5.6.4 Vital Signs, Other Physical Findings and Other Safety Data

5.6.4.1 Vital Signs

At Visit 1, 3 and B3, systolic and diastolic blood pressure are collected in the sitting, supine and standing positions. At all other visits, systolic and diastolic blood pressure are collected in the sitting position only.

Summaries will be presented by treatment arm for each vital sign parameter at each visit. Change from baseline to each post-baseline visit will also be presented.

Body mass index will be calculated, for each visit in which height and weight are recorded, as:

$$\text{Weight (kg)} \div \text{height (m)}^2$$

A separate table will be produced, by treatment arm and visit, presenting the incidence of patients with vital signs indicative of a medical condition at Visit 1 and indicative of an adverse event after Visit 1.

Based on the criteria presented in Section 8, clinically significant changes from baseline in vital signs measurements and other defined flagged values will be identified at each visit. The number of patients with a clinically significant change from baseline will be summarized by parameter, visit and treatment arm. The number of patients with at least one post-baseline flagged vital sign parameter value will be summarized by parameter, flagged criteria and treatment arm for the blinded phase and repeated for the OLE phase.

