5.6.4.6 Growth and Development

IGF-1 levels will be analyzed as part of the clinical laboratory testing. IGF-1 levels will be summarized on a continuous scale, including change from baseline, by treatment arm.

For the blinded phase only, change from baseline to the end of treatment visit for IGF-1 levels will also be plotted against the Tanner Stages, weight, and height recorded at baseline.

The pubic hair growth (both sexes), genital (males only) and breast (females only) development of all adolescent patients (i.e., 10 to less than 18 years of age at the time of signing the informed consent form, or earlier if clinically indicated by onset of menarche or other signs of precocious puberty) will be assessed using Tanner Staging. The patients will undergo a discreet physical examination and be assigned a value under each category of Pubic Hair Growth (both sexes), Genitals (male patients only), and Breasts (female patients only).

Tanner Stages will be summarized on a categorical scale, by treatment arm.

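### Height and weight are summarized raw and pooled over ages 1–65, so they are diluted evidence on growth under 18 in the blinded phase and cannot separate slowed growth from age mix in the OLE

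*SAP*

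**What the plan says.** SAP section 2.2 sets the blinded-phase objective "To evaluate the effect of GWP42003-P on growth and development (in patients less than 18 years old) compared with placebo". A parallel long-term objective, for the same age group, applies to the OLE.

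Section 3.3.2 lists two endpoints under Growth and Development in both phases, under headings that limit them to patients under 18. They are "Change in serum insulin-like growth factor-1 (IGF-1) levels" and change in Tanner stage, the latter for ages 10 to 17. Height and weight are not in that group. The OLE list names them under Safety and Tolerability, as physical-examination parameters.

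On reporting:

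- **Height and weight.** Section 5.6.4.3: "Height and weight will be summarized and listed together with the vital signs parameters". Section 5.6.4.1 summarizes each vital sign by arm and visit, and "Change from baseline to each post-baseline visit will also be presented". BMI is derived there. Appendix 6 places the tables on the safety set and the OLE safety set, with no version for under-18s or by age group.
- **Weight flag.** Appendix 2, Table 9 flags a weight change of 7% or more in either direction. Height has no flag.
- **IGF-1.** Section 5.6.4.6: "IGF-1 levels will be summarized on a continuous scale, including change from baseline, by treatment arm". Blinded-phase plots against baseline Tanner stage, weight and height are added.
- **Tanner stage.** Assessed from 10 to under 18 years, or earlier if clinically indicated, and tabulated by arm.
- **OLE columns.** Section 5.5.1 gives former GWP42003-P, former placebo, and overall.

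**The concern.** Raw change in height or weight in a child is mostly a function of age and sex. Without standardization, a mean change reflects the ages of the patients as much as any effect of treatment. Adults, who do not gain height, pull the pooled mean towards zero.

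The two named growth endpoints leave a gap. Below age 10, Tanner staging applies only if puberty appears early. The evidence for those children is then IGF-1 plus the pooled height and weight tables. The IGF-1 summary in section 5.6.4.6 does not repeat the under-18 limit and does not adjust for age and sex.

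At stake is the long-term question. If growth slowed during the OLE, the planned table would still show a positive mean change, and nothing in it would say how much gain was expected.

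**Working it through.** The plan has no figure for growth, height or weight, so there is nothing of its own to reproduce. The check has three parts. Age mix, growth velocities, SD and amount of slowing below are **assumptions that are not in the SAP**.

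**1. OLE height change**

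Time span: section 5.1.2 expects OLE Day 1 to fall on the end-of-treatment visit, Day 113. OLE Day 365 is then Day 113 + 364 = Day 477, which is 476 days after Day 1. Whether height is measured at that visit depends on a schedule not shown in the SAP.

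Assumed: equal numbers in the four age strata (1–6, 7–11, 12–17, 18–65), and 25% slowing in every child from Day 1. Pooled mean gain = mean velocity × 476/365, multiplied by 0.75 if slowed.

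| Assumed velocities (cm/year) | Mean | Normal growth | 25% slower |
|---|---|---|---|
| Low: 7/5/3/0 | 3.75 | +4.9 cm | +3.7 cm |
| Middle: 8.5/6/4/0 | 4.625 | +6.0 cm | +4.5 cm |
| High: 11/6.5/5/0 | 5.625 | +7.3 cm | +5.5 cm |

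Slowed growth under the high velocities (+5.5 cm) exceeds normal growth under the low ones (+4.9 cm). All six values are positive.

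Comparing the two OLE columns does not help much. Former placebo patients would slow only from Day 113. In the middle case their gain is 4.625 × (112 + 0.75 × 364)/365 = +4.9 cm, against +4.5 cm for former GWP42003-P. The difference, 4.625 × 0.25 × 112/365 = 0.35 cm, is the blinded-phase difference carried forward.

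**2. Blinded-phase height change**

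Same equal strata and middle velocities over 112 days (Day 1 to Day 113). Expected gains are 2.61, 1.84, 1.23 and 0 cm. A 25% slowing gives a mean difference of 0.355 cm over all ages and 0.473 cm in under-18s. The between-stratum variance of gain is 0.911 over all ages and 0.319 in under-18s. Within-stratum SD s is assumed to be 0.5 to 1.0 cm, in adults as well as children. Numbers per arm: 70 (section 3.2), or about 52 under 18 (three quarters of 70). Power ≈ Φ(difference/(SD × √(2/n)) − 1.96).

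| Comparison | SD, s = 1.0 | Power, s = 1.0 | SD, s = 0.5 | Power, s = 0.5 |
|---|---|---|---|---|
| All ages, raw | √(0.911 + 1) = 1.38 | 33% | √(0.911 + 0.25) = 1.08 | 50% |
| Under 18, raw | √(0.319 + 1) = 1.15 | 56% | √(0.319 + 0.25) = 0.75 | 89% |
| Under 18, age removed | 1.0 | 67% | 0.5 | over 99% |

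The SAP plans none of these tests. The table only measures how much information pooling loses. Restricting to under-18s recovers part of it and removing age recovers more.

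**3. Weight flag**

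At an assumed steady gain of 8% to 20% of baseline weight a year, +7% is reached after 0.07/0.08 × 365 = 319 days to 0.07/0.20 × 365 = 128 days. A child growing normally is therefore flagged before OLE Day 365, while a child who gains nothing is never flagged. The flag does not detect slowed growth.

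**The case against.** The strongest reply is that the SAP does not assign the growth objective to height and weight. It assigns it to IGF-1 and Tanner stage and treats height and weight as safety parameters. This is correct. A reader might infer from the height and weight tables that the growth objective cannot be answered at all; the documents do not support that, because the named endpoints address it in part.

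Several further points also stand:

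- The IGF-1 endpoint is headed under-18 in section 3.3.2, so its silence in section 5.6.4.6 is a matter of wording. The normal-range shift tables of section 5.6.3.1 may cover IGF-1 in part, although the SAP does not say so or state whether the ranges are specific to age and sex.
- Reporting is not confined to raw values and raw change. BMI is derived, weight has a percent-change flag, physical-examination findings indicative of an AE are tabulated, and individual values are listed.
- Growth is summarized by arm against placebo, and the objective does not call for a hypothesis test. Because randomization is stratified by age group, age does not bias the raw blinded-phase contrast on average. It costs precision.
- SD scores do not give the OLE a control. A falling score could reflect the disease or concomitant AEDs.

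These points limit the claim but leave the gap in place: no planned summary of height or weight takes account of age and sex or is confined to the population named in the objective. The SAP already repeats its AUC summaries by stratified age group (section 5.7.2), so age-specific reporting is not foreign to it.

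**Conclusion.** The point holds in limited form. Height, weight and BMI are summarized without age or sex adjustment over ages 1–65, and IGF-1 and Tanner stage cover growth under 18 only in part. The height and weight tables are diluted but unbiased evidence on growth in the blinded phase. In the OLE, with no concurrent control, they cannot distinguish slowed growth from age mix.

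The direction of this follows from the SAP alone. The sizes (about +6.0 against +4.5 cm by OLE Day 365, and the blinded-phase power figures) rest entirely on assumed age mix, velocities, SD and slowing, and should be read as illustration. They are not evidence that the drug slows growth. Growth lies outside the testing hierarchy in section 5.5.1, so no confirmatory conclusion is affected. This is a cheap and worthwhile improvement to the summaries.

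**What to change.** In SAP section 5.6.4.6, for patients under 18:

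1. Derive age- and sex-specific SD scores for height, weight and BMI at each visit where they are recorded, from a named growth reference.
2. Summarize change from baseline in these scores by arm and stratified age group in the blinded phase, and over time in the OLE.
3. State that the IGF-1 growth summary is limited to patients under 18, and express IGF-1 relative to the age and sex range.
4. Keep the existing raw vital-signs tables for safety.

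An ANCOVA of change in SD score in the blinded phase, with the model already used in section 5.5.3.2.4 (baseline, stratified age group, treatment arm), is optional.

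The cost is some SAP wording, one derivation and a few added tables. Age, sex, height and weight are already collected and listed. A growth reference has to be chosen and named, and the OLE remains uncontrolled, which the text should say.

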5.6.4.4 Columbia-Suicide Severity Rating Scale

The C-SSRS is completed for patients who are 6 years and older and capable of understanding and answering the questions, in the investigator's opinion. Questions are asked on suicidal behavior, suicidal ideation and intensity of ideation. At the screening visit, questions are in relation to lifetime experiences and all subsequent questioning in relation to the last assessment.

The following C-SSRS data will be summarized by treatment arm at each visit for patients in the safety analysis set:

- Incidence of the following suicidal ideation:
 - Wish to be dead.
 - Non-specific active suicidal thoughts.
 - Active suicidal ideation with any methods (not plan) without intent to act.
 - Active suicidal ideation with some intent to act, without specific plan.
 - Active suicidal ideation with specific plan and intent.
- Incidence of the following suicidal behavior:
 - Actual attempt.
 - Interrupted attempt.
 - Aborted attempt.
 - Preparatory acts or behavior.
 - Suicidal behavior.
 - Completed suicide.

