5.1.3 Definitions

5.1.3.1 Baseline

For clinic visit based endpoints, baseline is defined as the last record or measure collected prior to the first dose of IMP.

For IVRS based endpoints, baseline will include all available data from the day of Visit 2 to Day 1 of the blinded phase.

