Table 13.3.2	Shift Table for Biochemistry Laboratory Parameters – Based on Toxicity Limits	Safety Analysis Set
Table 13.3.3	Shift Table for eGFR – Based on Derived Grades	Safety Analysis Set
Table 13.4	Summary of Liver Parameter Flags	Safety Analysis Set
Table 13.5	Incidence of Laboratory Abnormalities	Safety Analysis Set
Table 13.6	Summary of Pregnancy Test and Urine THC Screen Results	Safety Analysis Set
Table 14.1.1	Summary of Vital Signs	Safety Analysis Set
Table 14.1.2	Incidence of Clinically Significant Changes from Baseline for Vital Signs	Safety Analysis Set
Table 14.1.3	Incidence of Defined Flagged Vital Signs	Safety Analysis Set
Table 14.1.4	Incidence of Vital Signs Abnormalities	Safety Analysis Set

Table Number	Title	Analysis Set
Table 14.2.1	Summary of ECG Parameters	Safety Analysis Set
Table 14.2.2	Incidence of Defined Flagged ECG Parameter Values	Safety Analysis Set
Table 14.2.3	Incidence of ECG Abnormalities	Safety Analysis Set
Table 14.3	Summary of Columbia-Suicide Severity Rating Scale by Type	Safety Analysis Set
Table 14.4	Incidence of Physical Examination Abnormalities	Safety Analysis Set
Table 14.5	Summary of Tanner Stages	Safety Analysis Set
Table 14.6	Summary of Menstruation Details	Safety Analysis Set
Table 14.7	Summary of Patients with Inpatient Hospitalizations due to Epilepsy	Safety Analysis Set
Table 14.8.1	Summary of Plasma Concentrations	Safety Analysis Set
Table 14.8.2.1	Summary of PK Parameters (Overall and by Age Group)	Safety Analysis Set
Table 14.8.2.2	Summary of PK Parameter Metabolite to Parent Ratio (Overall and by Age Group)	Safety Analysis Set
Table 14.9	Summary of Plasma Concentrations of Concomitant Antiepileptic Drugs	Safety Analysis Set
Table 14.10	Summary of Study Medication Use and Behavior Survey	Safety Analysis Set
Table 14.11.1	Summary of Supplemental Drug Accountability Form	Safety Analysis Set
Table 14.11.2	Summary of Supplemental Adverse Event Form	Safety Analysis Set
Table 14.11.3	Summary of Site Classification Form	Safety Analysis Set

Table 18 List of OLE Phase Tables

Table Number	Title	Analysis Set
OLE Table 1.1.1	Summary of Patient Disposition by Site	OLE Safety Analysis Set
OLE Table 1.1.2	Summary of Patient Disposition During by Country	OLE Safety Analysis Set
OLE Table 1.2	Summary of Overall Patient Disposition	OLE Safety Analysis Set
OLE Table 2	Summary of Important Protocol Deviations	OLE Safety Analysis Set
OLE Table 3.1	Summary of Demographic Data	OLE Safety Analysis Set

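### The C-SSRS is tabulated only visit by visit, so no planned table counts each patient once per phase, although the endpoint is a comparison of arms over 16 weeks

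*SAP*

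**What the plan says.** SAP Section 3.3.2 introduces the blinded-phase secondary endpoints with "The following endpoints will be compared between treatment arms over the 16-week, double-blind treatment period (all changes relative to baseline"). Under safety and tolerability, that list includes "Columbia-Suicide Severity Rating Scale (C-SSRS: 19+ years") and the children's version for ages 6 to 18, where applicable.

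Section 5.6.4.4 describes the planned output: "The following C-SSRS data will be summarized by treatment arm at each visit for patients in the safety analysis set". Five ideation types and six behavior entries follow. On recall it states: "At the screening visit, questions are in relation to lifetime experiences and all subsequent questioning in relation to the last assessment".

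Appendix 6 holds one C-SSRS table per phase, Table 14.3 and OLE Table 14.3, both titled "Summary of Columbia-Suicide Severity Rating Scale by Type". The other C-SSRS outputs are patient listings (14.4.1 to 14.4.3 and their OLE counterparts).

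**The concern.** The endpoint list promises a comparison of arms over the whole blinded period. For a rare safety event, the natural quantity is the number of patients per arm who had the event at any time after dosing began. The planned table splits that quantity by visit and by type. A patient may be positive at several visits and under several types, so the cells cannot be added up to a number of patients.

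A difference between arms could therefore be spread over many small cells. For example, five patients who are each positive at a different visit would never appear as more than one patient in any visit column. A reader who wants the by-arm total would have to rebuild it from the listings.

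A smaller matter is how the columns are read. Screening captures lifetime history, and each later visit captures only the time since the previous assessment. If both stand in one series, incidence would be expected to fall after screening in every arm for reasons unrelated to treatment.

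**Working it through.** The SAP states no figure for the C-SSRS, so there is none to reproduce. The check compares sections and then bounds what by-visit counts can tell.

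**Sections side by side**

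- Section 3.3.2: the C-SSRS is to be compared between arms over 16 weeks.
- Section 5.6.4.4 and Table 14.3: incidence by type, arm and visit. There is no row for any time after baseline and no row for new or worsened findings.
- Sections 5.6.4.1 and 5.6.4.2: vital signs and ECG each get a count of patients flagged at least once after baseline, by arm, for the blinded phase and again for the OLE.
- Section 5.6.3.1: liver tests get a treatment-emergent count, meaning a criterion absent at baseline and met at any later time.

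The SAP thus uses a phase-level patient count for comparable safety data but not for the C-SSRS.

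**What by-visit counts allow**

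Inputs:

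- Arm size N = 70 (Section 3.2).
- Visits after Day 1 up to end of treatment (Table 2): Visits 4 to 10, which is seven, or six without the telephone visit (Visit 8). The SAP does not show at which visits the C-SSRS is given, so six is an assumption and seven is shown as the alternative.
- Assumed count: n_v = 2 positive patients at each visit. This is illustrative and does not come from the SAP.

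Formula: the number of patients ever positive lies between the largest single-visit count and the smaller of N and the sum over visits, i.e. max(n_v) ≤ ever positive ≤ min(N, Σ n_v).

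- Lower bound (the same two patients each time): 2/70 = 2.9%.
- Upper bound, six visits (different patients each time): 6 × 2 = 12, and 12/70 = 17.1%.
- Upper bound, seven visits: 7 × 2 = 14, and 14/70 = 20.0%.

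The same by-visit table therefore fits a phase incidence that varies by a factor of 12/2 = 6 with six visits, or 14/2 = 7 with seven.

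**Recall windows**

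At any one visit, every arm has the same recall window, so comparing arms within a visit column is sound. Across columns, screening covers a lifetime and the others cover an interval since the last assessment. Only the screening column needs separate treatment for this reason.

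**The case against.** The strongest reply is that the sentence in Section 3.3.2 is a generic lead-in to a long, mixed list. Change from baseline cannot apply literally to some of its items, such as adverse events or abuse liability. By-arm incidence at successive visits is itself a descriptive comparison over the period, and Section 5.6.4.5 treats epilepsy hospitalizations in the same way. The C-SSRS listings show ideation, behavior and attempts for each patient. Suicidality reported as an AE enters the phase-level TEAE and serious TEAE tables, and it also triggers a Supplemental Adverse Event Form (Section 5.7.6).

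Much of this stands. No test or estimate is affected, no planned number becomes wrong, and a determined reader could recover the total from the listings. But the AE tables capture only what was reported as an AE. The special-interest terms in Appendix 1 cover abuse liability and name no suicidal ideation or behavior. For the supplemental form, only the number of patients with a completed form is summarized. None of these replaces a C-SSRS count by arm.

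Three stronger readings are tempting, and the SAP does not support them:

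- A reader might infer that the change of recall window is why the 16-week comparison is missing, or that it invalidates comparison of arms. It does neither. The comparison is missing because no phase-level row is specified.
- A reader might infer that the general baseline rule ("For clinic visit based endpoints, baseline is defined as the last record or measure collected prior to the first dose of IMP", Section 5.1.3.1) will make past ideation look new. No planned C-SSRS output uses a baseline, so nothing is misclassified as the plan stands.
- A reader might infer a large distortion from uneven visit spacing. Nominal gaps in the blinded phase are 14 to 28 days and are shared by all arms. Longer gaps occur only in the OLE, and the C-SSRS schedule is not in the SAP.

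**Conclusion.** The gap is real but modest. The SAP states a 16-week comparison of arms for the C-SSRS and specifies only by-visit tabulations, from which the number of patients affected per arm cannot be derived. The 2.9% to 17.1% range shows how wide the ambiguity can be. It rests on assumed counts and an assumed six assessments, and it is not a forecast. Same-visit comparisons between arms remain valid. The recall issue is limited to reading the lifetime screening column as part of the visit series. Because the summary is descriptive and listings and phase-level AE tables exist, priority is low to moderate. The reason to act is that the missing count uses data already collected.

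**What to change.** In Section 5.6.4.4, Table 14.3 and OLE Table 14.3, add for each phase, with the treatment columns already planned for that phase, the number and percentage of patients with:

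1. any post-baseline suicidal ideation;
2. any post-baseline suicidal behavior;
3. ideation or behavior that is new or worse relative to the pre-dose record, where that record includes the lifetime answers at screening.

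Use patients with at least one post-baseline C-SSRS assessment in the phase as the denominator, because the scale is given only to patients aged 6 or older who can answer it. State in the text that the pre-dose record for row 3 includes lifetime screening, so that the general baseline rule is not applied by default. Show the lifetime screening results in a separate block and not as the first column of the visit series. Keep the by-visit rows.

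The cost is a few extra rows in two descriptive tables and a short definition. No new data are needed, and the primary and key secondary analyses are untouched.
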